## 9 Treatment Plan

### 9.1 Methods of Assigning Subjects to Treatment Groups

This is a double-blinded study, in which the identity of the study drug will be unknown to investigator/evaluator and subjects, as well as all individuals closely associated with the study.

Subjects will be randomized to 1 of the 2 treatment groups in a ratio of 1:1 (IDP-120 [tretinoin 0.05% and benzoyl peroxide 2.5%] Gel: IDP-120 Vehicle Gel). Each screened subject will be assigned a unique 6-digit study subject number assigned by the investigational center, which will consist of the 3-digit investigational center/site number (pre-assigned by sponsor/designee) and the 3-digit chronological screening order number, starting with 001 (e.g., 101001, 101002). The study drug kits will be assigned to subjects based on a randomization code, and a kit will be dispensed to the subjects by the IWRS at Baseline, Week 4 and Week 8 visits. A study drug log will document the inventory and dispensing of study drug at each investigational center.

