## 12 Statistics

All statistical processing will be performed using SAS® version 9.3 or later unless otherwise stated. Statistical significance will be based on two-tailed tests of the null hypothesis resulting in p-values of 0.05 or less.

The primary method of handling missing efficacy data will be based on estimation using the method of Markov Chain Monte Carlo (MCMC) imputation. This method provides robust estimation when the pattern of missingness is arbitrary. Additionally, the estimation will be done

for each treatment group separately so that the pattern of missingness for one group does not influence the estimation of missing data for another group. Groups of complete datasets following the estimation will be concatenated to form analysis datasets for the comparative analyses and subsequent imputation result inference with SAS PROC MIANALYZE. Descriptive statistics will also be derived from the multiply imputed datasets.

Additionally, a model-based multiple imputation process will be used as a sensitivity analysis to the MCMC imputation. The absolute change in lesion count will also be analyzed using a repeated measures ANCOVA for lesion count data or a repeated measures logistic regression model (generalized estimating equations) for the dichotomized EGSS. Finally, a tipping point analysis will be performed for the primary endpoints.

A statistical analysis plan (SAP), describing all statistical analyses will be provided as a separate document. The SAP will be finalized prior to unblinding of the study treatments.

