**EGSS Missing Data Imputation**

A similar procedure will be used for the analyses based on percentage of EGSS successes wherein the ANCOVA analysis is replaced with a logistic regression analysis. Specifically, missing 12 week EGSS values from which the dichotomized EGSS is derived will be estimated by MCMC which does not rely on the assumption of data missing at random. Additionally, the pattern of missing observations in each treatment group cannot influence the missing value estimation in the other because the imputation is being conducted independently for each treatment group.

The missing 12-week EGSS values will be derived for the analysis using the method of Markov Chain Monte Carlo (MCMC) multiple imputation. Multiple imputation and subsequent analysis will involve 3 principal tasks:

1. Create a data set, one for each treatment group, of subjects with observed values and those needing estimation by MCMC. The missing EGSS values in each data set will be filled in using the MCMC method 5 times to generate 5 data sets. The resulting data sets for each treatment arm will be combined into one complete data set by imputation.

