**Syntax:**

```
proc mi data=datain out=dataout seed=&seed. nimpute=5 <options>;
  where trtpn=(1, or 2);
```

```

mcmc chain=multiple;
var baseline week2 week4 week8 week12;
run;

```

2. For each complete data set, the dichotomous success rate (clear or almost clear with a 2-point change from baseline) will be computed. The 12-week imputed EGSS values will be rounded to the nearest integer value prior to evaluating the success rate. Each complete data set will be analyzed with a logistic regression with factors of treatment group and analysis center.
4. The results from these analyses will be combined into a single inference using SAS PROC MIANALYZE.

A total of 2 random seeds will be needed to impute EGSS for the two treatment groups. Those 2 random seeds have been pre-specified by using a random number generator:

- EGSS; IDP-120 Gel: Seed= 923694678
- EGSS; IDP-120 Vehicle: Seed= 802843905

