### **12.8.2 Sample Size Determination**

These power calculations are based primarily on the observed Week 12 results of the Phase 2 study, V01-120A-201. This study was a four-arm trial including IDP-120 Gel versus its individual gel components and Vehicle Gel and is therefore a relevant study for powering the current study.

A sample size of 300 per treatment arm has greater than 99% power to detect a statistically significant difference in non-inflammatory lesions with a significance level of 0.05. The estimated absolute change from baseline in treatment means were 13.3 and 8.7 for IDP-120 Gel versus its Vehicle gel, respectively, with a standard deviation of 11.0.

A sample size of 300 per treatment arm has greater than 99% power to detect a statistically significant difference in non-inflammatory lesions with a significance level of 0.05 using the estimated absolute change from baseline in treatment means of 18.8 and 7.8 for IDP-120 Gel versus its Vehicle Gel, respectively, with a standard deviation of 16.4.

In order to achieve at least 95% power to detect a statistically significant difference in the percentage of subjects who have at least a 2 grade reduction at Week 12 from Baseline in EGSS and are Clear or Almost Clear with a significance level of 0.05, a sample size of 293 per treatment group is required. The estimated percentages with a 2 grade reduction at Week 12 from Baseline in the EGSS and Clear or Almost Clear are 26.6% and 14.3% for IDP-120 Gel versus its Vehicle Gel respectively. For simplicity, a sample size of 300 per treatment arm will be used.

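### Missing EGSS grades are drawn from a normal model and rounded, so the imputed success rate need not match the true one; the effect on the result is probably small, but it is avoidable

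*Combined protocol and SAP*

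**What the plan says.** Section 12 makes MCMC multiple imputation the primary handling of missing efficacy data. For EGSS, section 12.1.9 says "The missing EGSS values in each data set will be filled in using the MCMC method 5 times to generate 5 data sets". The work is done separately in each arm, with the statement "mcmc chain=multiple" and a variable list of EGSS at baseline and Weeks 2, 4, 8 and 12. Before success is evaluated, "The 12-week imputed EGSS values will be rounded to the nearest integer value prior to evaluating the success rate". Each completed data set is then analyzed by logistic regression on treatment and analysis center.

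Section 12.1.10 adds two EGSS sensitivity analyses that use no rounded values: a repeated measures logistic model (GEE) without imputation, and multiple imputation of the dichotomized score by logistic regression on treatment and center. It also announces a tipping point analysis without giving its method.

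**The concern.** EGSS is a five-level ordinal grade, and section 8.1 limits its baseline to 3 or 4. The MCMC statement treats all five visits as jointly normal. A rounded draw is a success when it lies below 1.5, so the imputed success rate is the area of a fitted normal curve below 1.5. That area equals the probability of grade 0 or 1 only if the grades happen to fit the curve, and nothing in the plan checks this. Imputation is by arm and the arms should have different grade distributions, so the error can differ between arms. It is systematic, so more imputations would not reduce it.

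It falls on the tightest co-primary endpoint. All three must be significant (section 12.1.6), and section 12.8.2 plans at least 95% power for EGSS against more than 99% for the lesion counts.

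**Working it through.** **Inputs from the protocol.** Success rates: "Clear or Almost Clear are 26.6% and 14.3% for IDP-120 Gel versus its Vehicle Gel respectively" (12.8.2). Two-sided alpha 0.05 (12). Allocation 1:1 (9.1). 300 per arm (12.8.2). Baseline grade 3 or 4 (8.1). **Not in the protocol, so assumed:** the Week 12 grade distribution, the missing fraction and the correlation between visits.

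**1. The plan's own figure.** The protocol says "a sample size of 293 per treatment group is required". With z-values 1.960 and 1.645 and mean rate 0.2045, the pooled formula gives

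n = [1.960·√(2·0.2045·0.7955) + 1.645·√(0.266·0.734 + 0.143·0.857)]² / 0.123² = 276.5.

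The continuity correction, (n/4)·[1 + √(1 + 4/(n·0.123))]², gives 292.5, which rounds up to 293. The figure reproduces. Uncorrected power at 300 per arm is 96.4%.

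**2. What counts as success.** From baseline 3 or 4, grade 0 or 1 is always a drop of at least 2. Success is therefore Week 12 grade ≤ 1, and an imputed subject succeeds when the draw is below 1.5. The text does not say what happens to draws that round below 0; they are taken as successes here.

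**3. Does the normal area match?** Take assumed Week 12 distributions with the protocol's success rates, compute mean μ and SD σ, and compare Φ((1.5 − μ)/σ) with the true rate. For the first row, μ = 0.236 + 2·0.33 + 3·0.374 + 4·0.03 = 2.138, σ = 0.912, and Φ(−0.700) = 24.2%.

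| Arm, % in grades 0/1/2/3/4 (assumed) | μ | σ | Normal area below 1.5 | True | Shift, points |
|---|---|---|---|---|---|
| Gel 3/23.6/33/37.4/3 | 2.138 | 0.912 | 24.2% | 26.6% | −2.4 |
| Gel 8/18.6/33/37.4/3 | 2.088 | 0.996 | 27.7% | 26.6% | +1.1 |
| Vehicle 2/12.3/20/60.7/5 | 2.544 | 0.845 | 10.8% | 14.3% | −3.5 |
| Vehicle 1/13.3/40/42.7/3 | 2.334 | 0.780 | 14.2% | 14.3% | −0.1 |

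Size and sign depend on shape. This check ignores earlier visits, which the planned step uses.

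**4. With earlier visits.** Correlated grade paths were simulated, Week 12 values were removed, and the normal-and-round step was applied within arm. Shifts are in points, among imputed subjects only.

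- Four assumed distributions, 13–23% missing. Vehicle peaked at grade 3: vehicle 14.2% became 10.9% (−3.3) and gel 26.7% became 23.8% (−2.9). More subjects fully clear: gel 26.8% became 28.9% (+2.1), with vehicle unchanged at 14.7%.
- Four other assumed distributions, about 18% missing: −2.1, +1.1, −2.8, −0.2.
- A broader set: gel about −5 to +1 (median −1.1), vehicle about −2 to +4 (median +0.8).

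**5. From imputed subjects to the whole arm.** Arm shift = shift among imputed × missing fraction.

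- −2.8 × 0.18 = −0.5; +1.1 × 0.18 = +0.2.
- −3 × 0.20 = −0.6; +2 × 0.20 = +0.4.
- Edges of the broader set: −4.9 × 0.20 = −1.0; +4.0 × 0.20 = +0.8.

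**6. Treatment difference.** In the first simulation the difference moved by −0.1 to +0.4 points (worst case 12.4 to 12.8). Another simulation used the same shape parameters in both arms. There the gel shift minus the vehicle shift was −1.9 to −3.4 points among imputed subjects in all 14 scenarios, which times 0.20 is −0.4 to −0.7 on the difference. The two disagree on sign.

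**7. Scale.** The standard error of the difference is √(0.266·0.734/300 + 0.143·0.857/300) = 3.25 points, so 0.4 points is 0.12 SE and 0.7 is 0.22 SE. If −3 fell on the gel and +2 on the vehicle at 20% missing, the planned difference of 12.3 would become 11.3 and power 93.2%. The reverse pairing gives 13.3 and 98.3%.

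**The case against.** The strongest reply is that the effect hardly matters. A few tenths of a point sits well inside sampling error. If the arms had the same grade distributions and the same missingness, the error would be equal in both and cancel, so no inflation of Type I error has been shown. The plan also has two analyses free of rounding, which would show whether the conclusion leans on the normal model. All of this stands, and it sets the severity.

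It does not remove the point. The sensitivity analyses leave the primary estimate as it is. The logistic imputation also leaves out Weeks 2, 4 and 8, so it differs from the primary method in two ways at once, and a discrepancy could not be attributed to rounding.

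A reader might infer that -3 to +2 points is the error in an arm's reported success rate, or a bound on it. It is neither: it applies only to imputed subjects, and other plausible distributions go beyond it. Even at -7.5, the extreme of a wide grid of assumed distributions, a 3-point arm shift needs 3/7.5 = 40% missing. A reader might also infer that the method favors the gel or works against it. The documents give nothing from which to settle the direction.

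One limit concerns the remedy. In simulation, imputing grades as categories kept the difference within about 0.1 point of the truth. That was a categorical hot deck in very large samples, not an ordinal logistic model at 300 per arm.

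**Conclusion.** The point holds, at low severity. Rounding normal draws of a 0–4 grade gives an imputed success rate that need not match the chance of grade 0 or 1, and the mismatch can differ by arm. Under the assumed distributions it is roughly -3 to +2 points among imputed subjects, and about half a point on a whole arm at around 20% missing (0.6 at the edge of that range, about 1 point under the broader set). The effect on the treatment difference is small and of unknown direction. None of these sizes can be derived from the protocol. The case for change is that a better-suited method costs little, not that the planned conclusion is in danger.

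**What to change.** In section 12.1.9, and in the SAP that section 12 says will be finalized before unblinding:

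- Replace the EGSS step with by-arm ordinal imputation: PROC MI FCS with an ordinal LOGISTIC model for EGSS at Weeks 2, 4, 8 and 12, using baseline and the other visits' EGSS. The two EGSS seeds can stay.
- Delete the rounding sentence.
- Lesion counts from observed earlier visits are an optional addition. Do not require Week 12 counts as predictors, since a subject who misses that visit usually lacks them too.
- Pre-specify a collapsing rule for sparse grades, such as 0 with 1 and 3 with 4. From baseline 3 or 4, neither merge changes who is a success or who has a 2-grade reduction.
- Keep the rounded MCMC analysis as a sensitivity analysis if wanted.

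The cost is wording and code. The downside is sparse extreme grades, mainly at early visits and in the vehicle arm, where 14.3% of 300 is only about 43 expected successes at Week 12. Where grades are merged, imputed frequency tables cannot show them separately. A trial run on simulated data at 300 per arm before unblinding would show whether the model fits.

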### 12.1.10 Sensitivity Efficacy Analyses

#### Sensitivity analyses for absolute change in lesion count

The first sensitivity analysis for absolute change in lesion count will use a repeated measures ANCOVA, with treatment, analysis center, and visit (ie, Week 4, Week 8) as independent factors and a covariate of baseline lesion count. In this analysis, data from all post-baseline visits will be included with no imputation for missing data.

The second sensitivity analysis will use the model based multiple imputation method to impute missing data for the absolute change in lesion counts at Week 12. Although the full details will be presented in the SAP, the multiple imputation will involve 3 principal tasks:

1. Missing values will be filled in 5 times to generate 5 data sets. The imputation model used will be an ANCOVA with factors of treatment group and analysis center, and a covariate of baseline lesion count (ie, the imputation model will be the same as the analysis model). Appropriate modifications will be made should the analysis be based on a non-parametric method.
2. Each complete data set will be analyzed with an ANCOVA with factors of treatment group, and analysis center, and a covariate of baseline lesion count.
3. Results from these analyses will be combined into a single inference using SAS PROC MIANALYZE.

A total of 2 random seeds will be needed. Those 2 random seeds have been pre-specified by using a random number generator:

- Inflammatory Lesion Counts: Seed= 1792696133
- Non-Inflammatory Lesion Counts: Seed= 1438330601

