### 12.1.7 Descriptive Statistics

Descriptive statistics will be presented for the following parameters by treatment group for both the ITT and PP populations:

- Frequency and percent distributions of the Evaluator's Global Severity Score at Baseline and Weeks 2, 4, 8, and 12.
- Frequency and percent distributions of the dichotomized Evaluator's Global Severity Score at Baseline and Weeks 2, 4, 8, and 12.
- Descriptive statistics including mean, median, standard deviation, minimum, and maximum will be used to summarize inflammatory and non-inflammatory lesion counts at Baseline and Weeks 2, 4, 8, and 12.
- Descriptive statistics including mean, median, standard deviation, minimum, and maximum will be used to summarize the absolute and percent change in inflammatory and non-inflammatory lesion counts at Weeks 2, 4, 8, and 12.

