#### Sensitivity analyses for EGSS

The first sensitivity analysis for the dichotomized EGSS success will use a repeated measures logistic regression model (generalized estimating equations), with dichotomized EGSS success as the dependent variable and treatment, analysis center, and visit (ie, Week 4, Week 8) as independent factors. In this analysis, data from all post-baseline visits will be included with no imputation for missing data.

The second sensitivity analysis will use the model based multiple imputation method to impute missing data for the dichotomized EGSS data. Although the full details will be presented in the SAP, the multiple imputation will involve 3 principal tasks:

1. Missing values will be filled in 5 times to generate 5 data sets. The imputation model used logistic regression with factors of treatment group and analysis center (ie, the imputation model will be the same as the analysis model).
2. Each complete data set will be analyzed with a logistic regression a factors of treatment group and analysis center.
3. Results from these analyses will be combined into a single inference using SAS PROC MIANALYZE.

A total of 1 random seed will be needed. The random seed has been pre-specified by using a random number generator:

- EGSS: Seed= 461039866

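### As written, the first sensitivity analysis of each co-primary endpoint estimates an effect pooled over visits, not the Week 12 effect

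*Combined protocol and SAP*

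**What the plan says.** All three co-primary endpoints are at Week 12 (Section 12.1.1; Synopsis, Efficacy Evaluation). Section 12.1.10 gives each endpoint type a first sensitivity analysis:

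- Lesion counts: a repeated measures ANCOVA "with treatment, analysis center, and visit (ie, Week 4, Week 8) as independent factors and a covariate of baseline lesion count".
- Dichotomized EGSS: a GEE logistic model with "treatment, analysis center, and visit (ie, Week 4, Week 8) as independent factors".

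For lesion counts the next sentence reads: "In this analysis, data from all post-baseline visits will be included with no imputation for missing data". The EGSS paragraph says the same. Under Evaluations and Analyses in Section 12, those visits are Weeks 2, 4, 8 and 12.

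The shorter description in Section 12 ("The absolute change in lesion count will also be analyzed using a repeated measures ANCOVA for lesion count data", with GEE for EGSS) adds no model terms. Section 12 also announces a further document: "A statistical analysis plan (SAP), describing all statistical analyses will be provided as a separate document". Inside Section 12.1.10, the explicit deferral ("Although the full details will be presented in the SAP, the multiple imputation will involve 3 principal tasks") is attached only to the second, multiple-imputation analyses.

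Section 12.1.7 will "summarize the absolute and percent change in inflammatory and non-inflammatory lesion counts at Weeks 2, 4, 8, and 12", and asks for "Frequency and percent distributions of the dichotomized" EGSS at Baseline and the same four visits.

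**The concern.** A model with treatment and visit as main effects has a single treatment coefficient. It is a weighted average of the visit-specific effects or, in the logistic model, a common odds ratio. Unless the effect is constant over visits, that is not the quantity tested in the primary analysis. It is hard to read the omission as shorthand, because the protocol names interactions where it wants them: treatment by analysis center in Sections 12.1.4 and 12.1.8, and treatment by site in 12.1.8.

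This is the specified analysis that uses the observed interim visits without imputation, so it is a natural cross-check on the imputed Week 12 result. As written, a smaller estimate could reflect speed of onset and not missing data, and the analysis alone cannot confirm the size of the Week 12 effect. Its estimate also moves with the amount of dropout, because dropout removes late visits.

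Separately, the parenthesis naming Weeks 4 and 8 contradicts the sentence after it. Read literally, it leaves out Week 12.

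**Working it through.** **What the model estimates.** Let the true treatment effects at Weeks 2, 4, 8 and 12 be d2, d4, d8 and d12. With complete data, the main-effects coefficient estimates the sum of w_v × d_v. The weights are proportional to V⁻¹1, where V is the within-subject covariance, which the protocol does not state. With equal variances, compound symmetry gives 0.25 per visit; AR(1) with correlation 0.7 gives about 0.385/0.115/0.115/0.385. The result is d12 for any weights only if the effect is constant.

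**The plan's own figures (Section 12.8.2; 300 per arm, two-sided 0.05).**

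- First lesion comparison: 13.3 − 8.7 = 4.6, SD 11.0. SE = 11.0 × √(2/300) = 0.898; z = 4.6/0.898 = 5.12; power = Φ(5.12 − 1.96) = 99.9%.
- Second: 18.8 − 7.8 = 11.0, SD 16.4. SE = 1.339; z = 8.21; power above 99.9%.
- EGSS: 26.6% against 14.3% at 95% power needs 293 per group with a continuity correction.

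All three agree with the protocol.

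**Assumed inputs.** The documents give no effects before Week 12, no dropout rate and no correlation. I assume compound symmetry with correlation 0.6, the same SD at every visit, and three onset curves, as percentages of the Week 12 effect at Weeks 2/4/8/12:

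- slow: 10/25/60/100
- central: 25/50/80/100
- fast: 50/70/90/100

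**No dropout, 4.6 lesions.** SE of the pooled effect = 0.898 × √((1 + 3 × 0.6)/4) = 0.751.

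| Curve | Share of Week 12 effect | Lesions | z | Power |
|---|---|---|---|---|
| Slow | (0.10+0.25+0.60+1)/4 = 0.4875 | 2.24 | 2.98 | 85% |
| Central | (0.25+0.50+0.80+1)/4 = 0.6375 | 2.93 | 3.90 | 97% |
| Fast | (0.50+0.70+0.90+1)/4 = 0.775 | 3.56 | 4.74 | 99.7% |
| Constant | 1 | 4.6 | 6.12 | >99.9% |

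Unequal weights do not remove the gap. On the slow curve the AR(1) 0.7 weights give 0.385×0.10 + 0.115×0.25 + 0.115×0.60 + 0.385×1 = 0.52.

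**With dropout (simulation).** The set-up was 300 per arm, 2,000 runs, generalized least squares with the generating covariance, and no baseline or center terms. Dropout was monotone after Week 2 and depended on the last observed change (logit slope 0.7 per SD). The vehicle mean was at 30/50/80/100% of its Week 12 value.

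| Dropout | Share, slow/central/fast | Power for 4.6 lesions |
|---|---|---|
| 15% | 45/60/75% | 78/95/99.6% |
| 25% | 43/58/74% | 72/94/99.5% |

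At 25% dropout the shares correspond to 2.0/2.7/3.4 lesions. For the 11.0-lesion effect the lowest power was 98.6% (slow, 25%).

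**Other covariances, 25% dropout (1,500 runs).** Compound symmetry 0.4 or 0.8 and AR(1) 0.6 or 0.8 gave shares of 42–46/57–59/72–75%. Slow-curve power for 4.6 lesions was 64–85%.

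**With treatment-by-visit added.** The Week 12 contrast recovered 99–101% of the true effect. That is expected by construction, since dropout was missing at random and the covariance was correct.

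**EGSS.** The planning rates give a Week 12 odds ratio of (0.266/0.734)/(0.143/0.857) = 2.17. The main-effects GEE gives a common odds ratio over visits. No early success rates are available, so I attach no size to the difference.

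**The case against.** The separate SAP is to describe all analyses, and the interaction, contrast and covariance are details a SAP would normally carry. It may already contain the correction, and I cannot rule that out. The protocol nevertheless states these models, and defers detail explicitly only for the second analyses.

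The protocol ties the second lesion-count analysis to Week 12 and gives the first no time point; an overall effect across visits is a legitimate supportive summary. True, but under a heading of sensitivity analyses for a Week 12 endpoint it does not check the size of the Week 12 effect.

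Little depends on this analysis. It carries no decision rule, and the primary test, Type I error control (Sections 12.1.6 and 12.8.5), the second sensitivity analyses and the tipping point analysis are untouched. The by-visit summaries would show a reader whether the effect changes over time. This stands and limits the severity.

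The sizes are assumed. A Week 12 SD is applied to every visit, and leaving out baseline understates power if baseline is prognostic. In every non-constant curve used, the pooled estimate is below the Week 12 effect, so a positive result would be conservative and its direction informative. Possible loss of significance is confined to the smaller lesion effect with slow onset. All of this stands.

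Finally, a Week 12 contrast for lesion counts uses much the same information as the primary imputation, and ordinary GEE is generally not valid when dropout depends on earlier outcomes. Both are fair. The second applies equally to the model as written, and the fix does not cure it.

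**Conclusion.** The point holds and should be fixed, but it does not threaten the primary conclusion. As written, both first sensitivity analyses estimate an effect pooled over visits and not the Week 12 effect, and their list of visits contradicts itself.

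The lesion-count figures are illustrations that rest on the assumed onset curves, correlation and dropout mechanism; a constant effect would give no gap. With slow onset and 25% dropout, power of about 72% for 4.6 lesions means this analysis could miss significance although the Week 12 effect is as planned. For 11.0 lesions power stays at about 98% or more throughout. Confidence is medium, because the separate SAP is not among the text reviewed.

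**What to change.** In both first-analysis paragraphs of Section 12.1.10:

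- list visit as Weeks 2, 4, 8 and 12, which also removes the contradiction;
- add treatment-by-visit;
- state the within-subject covariance for the ANCOVA and the working correlation for the GEE;
- prespecify the Week 12 treatment contrast as the reported sensitivity result, keeping the pooled estimate as an extra if wanted;
- for the GEE, add a rule for a visit at which an arm has no EGSS success.

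If the separate SAP already does this, only the protocol wording needs aligning. The change should be made before unblinding.

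The cost is wording and a few lines of code, with no new data and no change in sample size. The Week 12 contrast is less precise than the average: at correlation 0.6 its standard error is about 20% larger with no dropout (0.898/0.751 = 1.195) and 28% larger with 25% dropout, and 9–47% larger over the other covariances tried. If the effect really were constant, the pooled test would be the stronger one.
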